Despite multiple options for colorectal cancer (CRC) screening, including several proven to reduce CRC mortality, population-level participation rates are suboptimal. In 2015, it was estimated that only 62% of Americans aged 50-75 were up to date with screening, which is substantially lower than the 80% by 2018 screening goal set by the National Colorectal Cancer Roundtable and endorsed by the American Society of Gastrointestinal Endoscopy.¹ The US Multi-Society Task Force (USMSTF) recommends colonoscopy and fecal immunochemical testing (FIT) as Tier 1 screening tests,² but barriers to completing these tests have been well-characterized.³ For colonoscopy, patient barriers include an aversion to the bowel preparation process, loss of a workday, and the invasive nature of the procedure. For FIT, the main patient barrier is a reluctance to handle stool samples. Although blood-based tests are not currently recommended in the screening guidelines, they overcome all of these known barriers and may substantially improve adherence to screening. Epi proColon is an FDA-approved blood test that detects methylated Septin9 DNA, which is increased in individuals with CRC. The test is indicated for average-risk individuals who have declined guideline-recommended screening options, such as colonoscopy and FIT. Guidelines suggest that patients who decline these Tier 1 options should be offered Tier 2 or 3 options such as sigmoidoscopy, stool-DNA, CT colonography, and capsule colonoscopy. However, since these lower-tier tests face the same patient barriers as the Tier 1 tests and are less widely available, individuals who have declined both colonoscopy and FIT constitute the *de facto* target population for the blood test. Studies have shown that patients who are offered a choice between the blood test and FIT prefer and have higher compliance to the blood test,^{4,5} but it is unknown what proportion of "screen-resistant" patients who have declined *both* colonoscopy and FIT will accept the blood test. This is the crucial question that will determine the potential role of the blood test in the CRC screening landscape.

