In 2017, over 135,000 people in the US will be diagnosed with CRC and more than 50,000 will die from this disease—making it the third most common cancer in both men and women and the second leading cause of cancer death.⁶ A preponderance of data show that both colonoscopy and fecal occult blood testing substantially reduce CRC incidence and mortality.^{7–10} Despite these compelling statistics, only 62% of Americans were up to date with CRC screening in 2015, which is substantially below our national goal of 80% by 2018 and also falls short of screening rates achieved for breast (72%) and cervical (83%) cancer.¹ Of the two Tier 1 screening options recommended by the USMSTF, colonoscopy is by far the predominant screening modality; 96% of individuals who were up to date with screening reporting that they received lower endoscopy, compared to 11% for a stool-based test.¹¹ Yet from a patient perspective, neither of these two options is ideal. Colonoscopy requires dietary modification, bowel preparation, an invasive procedure, time off from work, and an escort for the majority of individuals who receive sedation. Despite the gastroenterology community’s continuous efforts to improve the patient experience through innovations such as low residue diet, split dose and smaller volume bowel preparation, and carbon dioxide, the suboptimal screening rate is proof that a substantial proportion of the population still refuses colonoscopy. Similarly, a segment of the population refuses FIT because they find the idea of providing a stool sample unhygienic and unappealing. Therefore, despite the existence of many CRC screening options, there is still an unmet need for a test that is non-invasive, does not require a bowel preparation, and does not involve handling stool. The Septin9 DNA blood test is the only FDA-approved test that fits this description. Septin9 is currently not recommended by the USMSTF as a screening option, but it is not intended to be offered to patients in place of the recommended options. Rather, the blood test is intended for patients who have declined the available options—usually for the reasons cited above—for whom a blood test would be an acceptable alternative. Thus, it is not a competitor to colonoscopy but may motivate more patients to participate in screening and ultimately undergo diagnostic colonoscopy after a positive test. Both national and VA screening rates have plateaued over the last few years, which suggests that a new strategy may be needed to further improve screening uptake. The Septin9 blood test may address an unmet need for patients and provide a much-needed boost to screening efforts. In this study, we will offer Septin9 to individuals who have previously declined both colonoscopy and FIT, which will allow us to measure the effect of the test in the real-world clinical situation in which it is indicated.

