Primary outcome: Screening rate in the intervention group vs. control group after 6 months.

Secondary outcomes:

A) Complete screening rate in both groups, which is defined as completion of the entire screening strategy. For colonoscopy, this requires cecal intubation and an adequate bowel preparation. For individuals who took Septin9 and FIT, positive results must be followed by a colonoscopy with cecal intubation and adequate bowel preparation.

B) Among individuals in the intervention group who had a positive blood test, proportion who completed a follow-up colonoscopy within 6 months.

C) Endoscopic and pathologic findings among individuals in the intervention group who had a diagnostic colonoscopy.

Aim #2: *To survey screen-resistant patients to understand their beliefs and attitudes about CRC screening and testing options.* Both intervention and controls groups will be invited to complete a brief questionnaire. Questionnaire questions are shown in the Table and are adapted from a previous study that offered both the blood test and FIT to patients who had refused screening colonoscopy.⁴ All response options will be presented in a multiple-choice format. The full questionnaire is shown in the Appendix.

Primary outcome: Demographic and health-related predictors of accepting the blood test in the intervention group.

Secondary outcomes:

A) Proportion of both groups who answered that they would be willing to take a blood test for colorectal cancer screening

B) The most commonly cited advantages of a blood test compared to colonoscopy and stool test in both groups

C) The most commonly cited reasons for not taking the blood test in the intervention group. In an exploratory analysis, we will stratify results by race/ethnicity, self-reported health, frequency of healthcare access, and self-perceived risk of CRC.

Table. Select Questionnaire Questions

Demographics
What is your age?
What is your race?
What is your ethnicity?
Health status and medical history
How would you rate your overall health?
How many visits have you had with your primary care doctor in the past year?
What do you think is your own risk of getting colorectal cancer?
Colorectal cancer testing
Have you ever had a colonoscopy? If so, when?
Have you ever had a stool-based test? If so, when?

PROTOCOL TITLE: Assessing the effect of offering a blood-based colorectal cancer screening test

Why did you decide not to do a colonoscopy when offered in the past 6 months?

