The proposed study contains minimal risk. All participants in the study are due for colorectal cancer screening and will receive a letter stating this and encouraging them to screen with either colonoscopy or FIT. These are considered standard of care clinical tests. For the intervention group, the blood-based screening test is also presented as an alternate option. This is a FDA-approved test, although it is currently not available in the VA. Individuals in the intervention group who choose to undergo the blood test would undergo a single blood draw. A final risk is that of breach in patient confidentiality.

15) Potential Benefits to Subjects

Nearly 20% of age-eligible veterans cared for at the VA NY Harbor Health Care System are not up-to-date on colorectal cancer screening. The introduction of a non-invasive test that also does not involve handling stool may increase participation in screening in this refractory population.

16) Vulnerable Populations

Vulnerable populations will not be enrolled.

17) Sharing of Results with Subjects

The study team will share the results of the blood test with patients by telephone or mail and notify their primary care physicians using a CPRS note.

18) Setting

Study recruitment and phlebotomy will be performed at the VA NY Harbor Health Care System. The lab assay will be performed offsite at a commercial laboratory because the equipment is not available onsite.

19) Resources Available

The Principal Investigator (PI) is a board-certified gastroenterologist and clinical researcher with expertise in colorectal cancer screening. He has master's level training in epidemiology and biostatistics and is able to perform all of the planned analysis.

The research assistant will be credentialed in phlebotomy and trained by the PI in principles of patient navigation.

The PI has the full support of the Epigenomics, which makes the blood-based test. Epigenomics has agreed to cover the cost of the study.

PROTOCOL TITLE: Assessing the effect of offering a blood-based colorectal cancer screening test

20) Confidentiality

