14) Have you ever had a stool-based test (e.g. fecal occult blood test/FOBT or fecal immunochemical test/FIT)?

Yes No (SKIP to 15)

14a) How long ago was your last stool-based test?

Less than 12 months More than 12 months

15) Why did you decide not to do a colonoscopy when offered in the past 6 months?

I don't want to take the bowel prep
I don't want to know if I have colorectal cancer
Colonoscopy is painful
I don't have time
I don't have an escort
I'm at low risk and don't need screening
Other
I wasn't offered the test in the past 6 months

16) What would make you change your mind and get a colonoscopy?

If the bowel prep were easier
If I knew colonoscopy can prevent cancer by removing pre-cancerous polyps
Overcoming my fears about colonoscopy
If my doctor recommended it
If I knew it wasn't going to hurt
If I had time/could get time off from work
If I could find an escort
Other
Nothing would change my mind

17) Why did you decide not to do a stool test (fecal immunochemical test/FIT) when offered in the past 6 months?

I don't want to handle stool
I don't want to know if I have colorectal cancer
The directions for the stool test was too complicated
I don't think a stool test is accurate
I don't have access to a toilet that's suitable for collecting the stool sample
Other
I wasn't offered the test in the past 6 months

18) What would make you change your mind and take a stool test?

If the directions for the stool test was easier to understand
If I knew the stool test was accurate
If I had access to a toilet that's suitable for collecting the stool sample
Other
Nothing would change my mind

PROTOCOL TITLE: Assessing the effect of offering a blood-based colorectal cancer screening test

19) Would you take a blood test to screen for colorectal cancer?

Yes No (SKIP to 22)

20) Why would you take the blood test?

A blood test is easy/convenient
 A blood test is not painful
 A blood test is accurate
 Other

21) What do you think are the advantages of a blood test compared to colonoscopy and stool test?

It's more convenient than a colonoscopy or a stool test
 I don't have to do any special preparation to take the test
 I'm used to getting blood tests
 I think blood tests are more accurate than other tests
 The test is done by a medical professional and I don't have to do anything myself
 Other

22) Why would you not take a blood test?

I don't like getting my blood drawn
 I don't think a blood test is as accurate as a colonoscopy or stool test

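### Item 21, which supplies Aim 2 secondary outcome B, does not name two of the three features by which the protocol defines the need for a blood test, so outcome B cannot rank them directly

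*Combined protocol and SAP*

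**What the plan says.** Section 8 (Study Endpoints) defines Aim 2 secondary outcome B as "The most commonly cited advantages of a blood test compared to colonoscopy and stool test in both groups". It adds: "All response options will be presented in a multiple-choice format". Section 11 (Data Analysis) says that the Aim 2 secondary outcomes will be summarised descriptively.

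Item 21 of the appendix questionnaire asks: "What do you think are the advantages of a blood test compared to colonoscopy and stool test". Its substantive answers cover greater convenience, no special preparation, familiarity with blood tests, greater accuracy, and having a professional carry out the test so that the patient need do nothing. The sixth answer is Other.

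The rationale for the test appears in three places:

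- **Opening section (aims).** For stool testing: "For FIT, the main patient barrier is a reluctance to handle stool samples". For colonoscopy: "patient barriers include an aversion to the bowel preparation process, loss of a workday, and the invasive nature of the procedure". The same section also expects the convenience of a blood test to widen participation.
- **Section 3 (Background).** "there is still an unmet need for a test that is non-invasive, does not require a bowel preparation, and does not involve handling stool".
- **Section 15 (Potential Benefits to Subjects).** "The introduction of a non-invasive test that also does not involve handling stool may increase participation in screening in this refractory population".

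**The concern.** A ranking of cited advantages can contain only what the form lets people cite. Section 15 expects benefit from two features, non-invasiveness and no stool handling, and these are the two that item 21 does not name. Someone who values the blood test because it avoids stool or an invasive procedure has to choose a broader answer that also covers other reasons, or Other.

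Aim 2 exists to learn what people who have declined both tests think of the options. As the form stands, outcome B could be reported with no category for the barrier that the protocol calls the main one for FIT, and a reader could not tell whether respondents thought it unimportant or were not offered it. Section 23 describes the questionnaire as anonymous, so returning to respondents for a missing answer would be impractical.

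**Working it through.** No sample-size or power figure bears on this point, and the plan gives none for outcome B. The check is a comparison of texts.

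**Step 1. Which item feeds outcome B?** Of the items available for review (14 to 23), only item 21 asks for advantages over colonoscopy and stool testing, in almost the same words as outcome B. The table of selected questions in Section 8 also has just one advantages question, and it matches item 21. The part of the form before item 14 was not available, so this is confirmed for the visible items only.

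**Step 2. Match the three Background features to the item 21 answers.**

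| Feature in Section 3 | Answer in item 21 that names it | Nearest broader answer |
|---|---|---|
| No bowel preparation | Yes: no special preparation | not needed |
| No stool handling | None | Done by a professional; convenience; Other |
| Non-invasive | None | Convenience; Other |

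Named: 1 of 3. Not named: 3 − 1 = 2 of 3.

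**Step 3. Try a more generous match.** If the done-by-a-professional answer is credited as an indirect match for not collecting one's own stool, the count becomes 1 + 1 = 2 of 3. Non-invasiveness is still unmatched.

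**Step 4. Do neighbouring items fill the gap?**

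| Item | What it records | Why it is not outcome B |
|---|---|---|
| 15 | Pain as a reason for declining colonoscopy | A reason for refusal; pain is narrower than invasiveness |
| 17 | Unwillingness to handle stool as a reason for declining FIT | A reason for refusal, not an advantage of the blood test |
| 20 | Lack of pain as a reason to take the blood test | No comparison with colonoscopy or stool testing |

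Item 17 shows that the form already has wording for the stool reason. No visible item names invasiveness.

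**Step 5. Can the number affected be given?** No. The documents give no expected questionnaire response rate and no expected frequency for either view. Those who answer No at item 19 are sent to item 22 and never see item 21. The 170 per group in Section 11 is the Aim 1 sample size, not a count of people answering item 21.

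**The case against.** The strongest reply has four parts.

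- **Convenience is also part of the rationale.** The opening section names it, and lists a lost workday among the colonoscopy barriers. Item 21's convenience answer therefore measures something the protocol cares about. This stands: the two-of-three count applies to the Background's definition of the unmet need, not to every reason the protocol gives.
- **The existing answers are not empty.** The done-by-a-professional answer contrasts with collecting one's own sample, and Other is available. This stands in part. That answer mixes stool avoidance with effort and trust in professionals, and does not touch invasiveness. A write-in line beside Other may have been lost in text extraction. If there is one and it is coded, some of the information could be recovered. A reader might infer that the two features would be recorded as absent whatever their true frequency; the documents do not support that.
- **Other items carry related content.** Stool aversion in item 17 can be cross-tabulated with willingness in item 19 on the same form. This stands as indirect evidence, but the plan describes no such analysis, and it would not put the feature into outcome B's ranking.
- **The stakes are modest.** Outcome B is secondary and descriptive. The Aim 1 primary outcome is the six-month screening rate by group, and the Aim 2 primary outcome concerns demographic and health-related predictors of acceptance. Neither uses item 21. This stands in full.

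**Conclusion.** The point holds in a limited form. Two of the three features in the Background's definition of the unmet need have no answer that names them in item 21. On the generous match, one of three still has none. Outcome B therefore cannot rank stool avoidance or non-invasiveness directly, and its ordering may partly reflect the answers on offer.

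Two stronger readings are tempting but not supported. A reader might infer that convenience is bound to be overstated. The affected respondents could spread over several answers, and the visible form does not show whether more than one may be ticked, so the direction and size of any distortion are unknown. A reader might also infer that the trial loses its ability to test why the blood test works. The protocol does not give outcome B that role, and the primary outcomes of both aims are untouched.

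The conclusion assumes that outcome B is read from item 21 and that the unseen part of the form has no second advantages question.

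**What to change.** Before the questionnaire is used, add two answers to item 21: *I don't have to handle stool* and *It is not an invasive procedure*. Keep all existing answers and Other. Report the two new answers as separate categories in outcome B.

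The documents do not say whether forms have been sent. If they have, state in the report that outcome B ranks only the listed answers, and present item 17 (stool handling) and items 15 and 20 (pain) alongside it as indirect evidence.

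The cost is two lines on the form and a minor IRB update. There may be some loss of comparability with the questionnaire from which this one was adapted; how much cannot be judged, because the source wording is not in the documents. Sample size and the primary analyses do not change.
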